Targeting insomnia may become a promising intervention to prevent depression among youth, as Insomnia and depression are highly comorbid conditions, with increasing evidence suggesting their intricate, bidirectional relationship. In particular, insomnia and depression often co-occur, with 35-47% of individuals with insomnia having clinically significant depression and 60-84% of people with MDD experiencing comorbid insomnia symptoms.¹² Rather than a symptom of depression, insomnia is an independent problem which commonly precedes the development of depression,¹³ and has been found to increase the risk of developing incident new depression,^{14, 15} lead to poorer treatment response,¹⁶ increase the susceptibility of having recurrence,¹⁷ and represent an independent risk factor for suicidal ideation and behaviour.¹⁸⁻²⁰ This growing body of

evidence emphasise the unique, independent role of insomnia in the course of MDD, and interventions which directly target insomnia are most likely to improve depression outcomes, or may even prevent depression.

The mechanisms underlying the comorbidity of depression and insomnia have provided clues for further validating the preventive effect of insomnia treatments on depression. In biological domain, the most widely adopted theory is hyperarousal theory.^{21, 22} Evidence has clearly shown that stress-activated hypothalamic-pituitary-adrenal (HPA) axis hyperactivity exists in both depressed and insomniac patients. ²³⁻²⁵ Moreover, arousal responses of HPA axis is associated with slow wave sleep deficit and sleep continuity disruption in both depression and insomnia.²⁶⁻²⁸ In psychological domain, maladaptive cognitions and behaviors, such as worry, ruminations, vulnerability to stress and poor problem solving skills, are implicated in the association between depression and insomnia.^{22, 29} Additionally, a temporal relationship between depression and insomnia also favours the idea that effective treatment of insomnia would lower the risk of depression. As mentioned above, the occurrence of insomnia commonly precedes depression in most cases, and several longitudinal studies have demonstrated that previous insomnia was related to subsequent onset of depression.³⁰⁻³³ A meta-analytic review revealed that insomniac patients without depression at baseline have a twofold risk to develop depression.¹⁵ These evidences further indicated that insomnia could play a causal role in the onset of depression.²⁶

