Youth in e-CBT-I group will have fewer insomnia symptoms, depressive symptoms, suicidal ideation, plans and attempts than those in control group at each timepoint.
 Changes in candidate factors including insomnia symptoms, mood symptoms, circadian rhythms and sleep parameters will mediate the outcomes.

Recruitment and Screening

Potential participants will be recruited from colleges and senior secondary school in Hong Kong and mainland China and will be identified from various sources. These will include the local partner schools in Hong Kong established from our previous research projects. Partner schools in mainland China will be recruited by our collaborators with the school links in mainland China. Through our partner schools, students will be introduced to this study, and they will be asked to return the signed informed consents and leave their contact (e.g., email) in the reply slip to the research team if they are interested in taking part in the study. Furthermore, potential participants will be recruited through community referrals and advertising via social media and emails in Hong Kong and mainland China. Interested participants will be asked to complete the screening assessments, including Patient Health Questionnaire-9 (PHQ-9)⁵⁵ and Insomnia Severity Index (ISI)⁵⁶ via an online portal (Qualtrics). Participants who have an ISI score of no less than 15 and a PHQ-9 score between 4 and 20 will be further invited for diagnostic interview through telephone to screen for insomnia (International Statistical Classification of Diseases and Related Health Problems10th Revision Classification of Mental and Behavioral Disorders, ICD-10 Classification of Mental and Behavioral Disorders ⁵⁷), MDD and suicidality including ideation, plans and attempts (Mini International Neuropsychiatric Interview, MINI ⁵⁸). A potential participant who meets the inclusion criteria (see below) will be eligible to take part in the study.

Participants

Inclusion criteria and exclusion criteria for participants are as follows:

Inclusion criteria

- 1. Native Han youth in Hong Kong and mainland China, aged between15-25
- 2. A diagnosis of insomnia disorder measured by ICD-10 Classification of Mental and Behavioral Disorders
- 3. The presence of moderate or severe insomnia measured by a score of 15 or above on ISI
- 4. The presence of subclinical depression assessed by a score of more than 4 but less than 20 on PHQ-9
- 5. Access to smartphones

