- 6. Ability to read and understand research protocol

Exclusion criteria

- 1. Shift workers
- 2. The presence of prominent suicidality (suicide plans and suicide attempts) measured by MINI via telephone interview
- 3. A clinical diagnosis of psychosis, schizophrenia, bipolar disorder, or neurodevelopmental disorders

- 4. Current medical conditions that could cause poor sleep quality and sleep continuity disruption, such as eczema
- 5. The presence of current MDD or a prior episode of MDD within past two months measured by MINI via telephone interview
- 6. Women during pregnancy or lactation
- 7. Currently receiving psychological treatment for insomnia provided by a psychologist and/or pharmacological treatment for depression

Intervention

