The e-CBT-I will be delivered by a mobile application (eSleep) which contains a digital, self-paced, and highly interactive programme. The Chinese version (simplified Chinese/Mandarin) of the application has been designed to adapt for the language background of the participants in China. The program is developed as based on wellestablished CBT-I treatment protocol and consists of six 20-30 minutes sequential modules unlocked weekly with animated elements, including an overview of sleep, sleep restriction, stimulus control, cognitive therapy, structured worry time and relapse prevention. During sleep restriction module (session 2), participants will obtain a "sleep prescription" from the application, specifying their sleep window (from initial bedtime to final arising time) for the next seven days. The setting of the sleep window is based on individual's average total sleep time from the previous week, while adhering to the 5hour minimum rule. The sleep prescription is adjusted weekly based on the following criteria: 1) if sleep efficiency > 85%, increase sleep window by 15-20 min; 2) if sleep efficiency < 80%, decrease sleep window by 15-20 min; and 3) if sleep efficiency is between 80%-85%, keep sleep window the same. The application control management system provides online analytics, which allows the researchers to monitor individual's participation during the intervention by assessing how many sessions were completed and the number of weeks to complete the course. Participants will have access to the e-CBT-I treatment for 12 weeks, allowing them additional time to complete the intervention in case they were unable to completed it within the initial 6-week period. Individualized text messages will be sent to the participants regularly, asking them to complete the treatment sessions and sleep diaries on time. The participants will also be contacted weekly to prevent possible dropout from occurring during the intervention. The PI and collaborators have had the research and clinical experiences in delivering CBT-I, and the e-CBT-I treatment protocol has been tested and modified from our previous studies [Trial registration: clinicaltrials.gov Identifier: NCT03438331; funded by Early Career Scheme, Ref. 27613017] 59.

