The HE, a psychoeducation/information-approach, delivered in control group has been adopted in the previous study ⁵⁰. It also consists of six consecutive sessions which contains information about general sleep knowledge, functions of human organs, nutrition, environmental health, brain health, identification and treatments of common diseases, but the contents are not related to any active therapeutic components of CBT-I. Each module was unlocked weekly, and participants will have access to the intervention for 12 weeks. The general sleep knowledge session was purposively added in this sleep related RCT to meet the expectation of the participants. Individualized text messages will be sent to the participants regularly to remind them of completing the sessions and sleep diaries on time. The participants will also be contacted weekly to prevent possible dropout from occurring during the intervention.

Assessments

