The primary outcomes include remission rate of insomnia disorder conformed by ICD-10 Classification of Mental and Behavioral Disorders, change of insomnia symptoms measured by ISI, occurrence of MDD conformed by MINI and change of depressive symptoms measured by PHQ-9. Secondary outcomes include incidence of suicidality which includes plans and attempts as measured by MINI and change of anxiety symptoms measured by GAD-7. Other pre-specified outcome include incidence of suicidal ideation measured by BSSI, change of daytime symptoms measured by MFI, change of sleep-related thoughts and behaviors measured by DBAS-16, change of circadian rhythms measured by 7-Day Daily Sleep Diary and MEQ, and change of sleep parameters including time in bed (TIB), total sleep time (TST), sleep onset latency (SOL), wake after sleep onset (WASO), sleep efficiency (SE) measured by 7-Day Daily Sleep Diary.

Sample Size Estimation

The sample size calculation was based on the occurrence of diagnosed depressive disorder because the primary aim of the current study was to prevent clinical depression. According to the previous meta-analysis, the incidence rate of depression is approximately 11% in the individuals with insomnia ¹⁵. As the study sample included a mixture of individuals without prior depression and those with a history of MDD, an expected 50% increase in the cumulative one-year occurrence of diagnosed depressive disorder is anticipated (16.5%). Based on the previous research on CBT-I and our trial data on sleep-focused treatment for depression, a 50% reduction of occurrence rate is expected for the intervention group. Power analysis using Stata suggested that a total of 282 participants per condition would be required to achieve a power of 0.80 whilst allowing a type I error of 0.05 detect a hazard ratio of 0.5 under 1:1 randomization. In view of the attrition rate from previous study (40%), a total of 940 participants would be required (470 participants in each group x 2 groups). A protocol amendment was submitted to reduce the sample size to 708 (354 per group) based on an estimated attrition rate of approximately 20%, as it was determined that the attrition rate was lower than initially expected.

Data Analysis

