All main analyses will be based on the intent-to-treat (ITT) approach. We aim to obtain full follow-up data on every participant, but missing data may be inevitably expected due to withdrawal, loss-to-follow-up, or non-response questionnaire items. Baseline characteristics will be presented as percentage for categorical variables and as means (standard deviations) for continuous variables. The primary and secondary outcomes with continuous variables will be examined by using linear mixed-effects model (LMM) analysis. The changes of efficacy indicators (e.g., PHQ-9) from baseline to each follow-up time points and intervention differences were tested by the MIXED module of Stata, with major measures at each time point nested within each participant. Interaction effects of group by time will be examined to compare the effects of treatment on the major outcomes. Between-group difference in the estimated mean change from baseline to each time points from mixed models and Cohen's d will be used to calculate effect sizes. Current MDD will be analyzed by the survival analysis and the Mentel-Cog log rank test. An observation will be right censored to the day after the last point of interview when a participant is no longer eligible to experience a depressive episode, e.g., lost to follow-up or completed the trial without experiencing a depressive episode (12month follow-up after intervention). The effect of the intervention on insomnia remission will be analyzed using generalized estimating equations (GEE). The GEE analysis will be conducted by using the XTGEE module of Stata. Mediation analysis using maximum likelihood estimation within a structural equation modeling framework will be used to determine which outcomes are mediated by changes in candidate factors including sleep symptoms, mood symptoms, sleep-related unhelpful thoughts and maladaptive behaviors, circadian rhythm disruption and sleep parameters at follow-up. Sensitivity analyses will be conducted using imputation methods to examine the robustness of the results based on

different assumptions about the missing data. Strata variables (sex and insomnia severity) at baseline will be included as covariates in all analyses. Variables with a p value ≤ 0.05 will be considered statistically significant.

Ethics & Other Considerations

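### PHQ-9 change, a primary outcome, includes a sleep item, so a benefit confined to sleep can appear as fewer depressive symptoms, and no planned analysis separates the two

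*Combined protocol and SAP*

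**What the plan says.** The Outcomes section lists four primary outcomes: ICD-10 insomnia remission, ISI change, and "occurrence of MDD conformed by MINI and change of depressive symptoms measured by PHQ-9". Under Data Analysis, continuous outcomes go into a linear mixed model: "The changes of efficacy indicators (e.g., PHQ-9) from baseline to each follow-up time points and intervention differences were tested". No score with an item removed is mentioned. The sensitivity analyses described there concern missing data only. The same section plans a structural equation mediation analysis with sleep symptoms and sleep parameters among the candidate mediators. The Introduction names change in depressive symptoms as the outcome to be explained.

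The sample is selected for insomnia. Besides an ICD-10 diagnosis, the inclusion criteria require "The presence of moderate or severe insomnia measured by a score of 15 or above on ISI". They also require "The presence of subclinical depression assessed by a score of more than 4 but less than 20 on PHQ-9", again on the total score.

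The arms differ in whether they treat sleep. The Intervention section gives the e-CBT-I modules as "including an overview of sleep, sleep restriction, stimulus control, cognitive therapy, structured worry time and relapse prevention". Of the health education control it says that "the contents are not related to any active therapeutic components of CBT-I".

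**The concern.** PHQ-9 scores nine symptoms from 0 to 3, and one of them is sleep disturbance. This is a property of the named instrument and is not written in the protocol. In this sample that item is likely to be raised at entry. It is also the symptom that one arm treats and the other does not.

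The trial asks whether treating insomnia reduces depression. A fall in the sleep item with mood unchanged would count towards a yes on PHQ-9, although sleep benefit already has two primary outcomes of its own. The weight of the item depends on the starting score. At its maximum of 3 it makes up 3/5 = 60% of a total of 5 and 3/19 = 16% of a total of 19, the two ends of the entry window.

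The mediation analysis has the same problem. With insomnia or sleep as mediator and the PHQ-9 total as outcome, part of any mediated effect is sleep explaining sleep.

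**Working it through.** **The plan's own sample size.** This sets the scale and is not in dispute. Inputs from Sample Size Estimation: control occurrence 16.5%, hazard ratio 0.5, power 0.80, type I error 0.05 (taken as two-sided).
- Events (Freedman): ((1 + 0.5)/(1 − 0.5))² × (1.960 + 0.842)² = 9 × 7.849 = 70.6.
- Treated occurrence: 1 − 0.835^0.5 = 8.62%. Mean of the arms: (16.5% + 8.62%)/2 = 12.56%.
- Per arm: 70.6/(2 × 0.1256) = 281.2, so 282 as stated.
- With attrition: 282/0.6 = 470 as stated; 282/0.8 = 352.5, so 353 against the stated 354.
- Expected completers: 354 × 0.8 = 283 per arm, used below.

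**PHQ-9: an effect on the sleep item only.** The between-arm effect on the total is the sleep-item effect plus the effect on the other eight items. Set the second to zero. The documents give no PHQ-9 SD and no item data, so the SD (4 to 6) and the sleep-item difference (0.5 to 1.0 point) are assumptions.

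Formulas: SE = SD × √(2/283); power = Φ(difference/SE − 1.96) + Φ(−difference/SE − 1.96).

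| Assumed SD | SE | Difference reaching p = 0.05 | Power, 0.5 point | Power, 0.75 point | Power, 1.0 point |
|---|---|---|---|---|---|
| 4 | 0.336 | 0.66 | 32% | 61% | 84% |
| 5 | 0.420 | 0.82 | 22% | 43% | 66% |
| 6 | 0.504 | 0.99 | 17% | 32% | 51% |

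The standardised effects run from 0.5/6 = 0.08 to 1.0/4 = 0.25. This is a simple two-group comparison at one time point. It ignores the repeated measures and covariates of the planned model, so it gives an order of magnitude only.

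**Mediation.** In the same scenario the whole effect on the total is the sleep-item effect. Insomnia change would then account for much or all of it, and the model would report mediation of a depression benefit although the other eight items had not moved. No separate figure can be given without item data.

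**MINI MDD.** Again by the nature of the instrument, sleep disturbance is one symptom in a count and cannot make the diagnosis alone. It matters only for someone exactly at the threshold. Let f be the share of cases at the threshold only through sleep, and g the share of those in whom treatment removes that symptom. Occurrence becomes 16.5% × (1 − f × g).
- f = 0.2, g = 0.3: 16.5% × 0.94 = 15.5%, a relative fall of 6%.
- f = 0.3, g = 0.5: 16.5% × 0.85 = 14.0%, a relative fall of 15%.

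A two-proportion test with 283 per arm detects these in about 6% and 13% of trials. A wider range (f 0.1–0.4, g 0.2–0.5) gives hazard ratios of 0.98 to 0.79 and power of at most about 20%. The plan assumes a 50% reduction.

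**The case against.** The PHQ-9 total is the conventional score, and sleep disturbance can be a genuine symptom of depression, so removing it discards some real effect. This stands. It is why the total should remain primary and the shorter score should be a companion.

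The illustration rests on assumed inputs. The control arm is also not inert for sleep: it has a session on general sleep knowledge, sleep diaries and weekly contact, so the gap on the sleep item could be smaller than assumed. Both points stand. They limit what can be said about size, but not the absence of an analysis that would show it.

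Blinded interviews do not help with PHQ-9, which participants complete themselves online.

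A reader might infer two stronger points that the documents do not support.
- One is that MINI MDD is exposed to the same degree. The exclusion criteria rule out "The presence of current MDD or a prior episode of MDD within past two months measured by MINI via telephone interview", so insomnia at entry was not enough for a diagnosis and a new case must add other symptoms. The calculation above shows a small effect.
- The other is that the outcomes contradict the background statement, "Rather than a symptom of depression, insomnia is an independent problem which commonly precedes the development of depression". That sentence concerns the timing and causal role of insomnia. It does not say that sleep should be left out of depression scoring.

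**Conclusion.** The point holds for PHQ-9 and for mediation models with insomnia or sleep as mediator. As planned, a reduction in depressive symptoms cannot be told apart from improvement in the one sleep item. A difference of 0.5–1.0 point on that item alone would give a significant PHQ-9 result in about 17–84% of trials, assuming an SD of 4–6 and 283 per arm. The width of that range reflects the lack of item data in the documents. The missing companion analysis is certain; the size of the effect is not.

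For MINI MDD, the endpoint on which the trial was sized, the effect is minor: on assumed inputs, 16.5% falls to between 14.0% and 15.5%. The overlap could add a little to a real effect but is very unlikely to produce a hazard ratio of 0.5 alone. The sample size is unaffected.

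**What to change.** Keep the PHQ-9 total as the primary outcome and add to Data Analysis:

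1. The same linear mixed model fitted to PHQ-9 without the sleep item (eight items, range 0–24), as a pre-specified companion analysis.
2. That score as the outcome in every mediation model in which insomnia or sleep is the mediator.
3. A rule for interpretation: an effect on depressive symptoms beyond sleep is claimed only if the estimate without the sleep item also favours e-CBT-I with a confidence interval excluding zero. Failing the rule limits the claim; it does not show that mood was unaffected.

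Optionally, if MINI item responses are kept as well as the diagnosis, report a sensitivity count of MDD without the sleep symptom. Its symptom threshold must be fixed in advance, because keeping or lowering the threshold defines different diagnoses.

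The cost is a few sentences in the plan, re-runs of models already planned, and a check that PHQ-9 item responses are retained. Sample size, visits and treatment do not change. The downside is that the depression effect without the sleep item may be somewhat smaller, and that analysis sets aside some genuine depressive sleep change.

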To address the limitations in the existing literature, we propose to conduct a RCT of targeted prevention intervention to validate the treatment effect of e-CBT-I on insomnia disorder and examine whether digitally delivered insomnia treatment can reduce the risk of depression in a high-risk group of youth population. To further explore the mechanisms underlying the association between insomnia treatment and depression, we will evaluate whether changes in candidate factors including insomnia symptoms, mood symptoms, sleep-related unhelpful thoughts and maladaptive behaviours, and circadian rhythm disruption will mediate the changes in depressive symptoms. On a conceptual level, the proposed interventional study will also allow us to further test the causal pathway between sleep disturbance and major depression, by intervening and treating insomnia as a preventive measure of depression. On a pragmatic level, digital approach to insomnia intervention for prevention of youth depression, if effective, may have important public health implications given its high accessibility to the young populations.

Methodology

Study Design

A randomized, assessor-blind, parallel group-controlled trial will be conducted in youth with insomnia and subclinical depression. All qualified participants will be randomly assigned via online system to receive e-CBT-I or health education (HE). Randomization will be stratified by sex and the severity of insomnia. Assessments will be carried out at baseline, post-treatment, 6-month follow-up and 12-month follow-up. Additional assessments will be given upon the completion of sessions 2 (post-session 2) and 4 (post-session 4) to evaluate sleep symptoms, mood symptoms, circadian rhythms and sleep parameters of participants. Saliva collection kit will be mailed to participants at baseline to collect their salivary cortisol and DNA, and at 12-month follow-up to collect their salivary DNA. Semi-structural individual interviews about user experience and satisfaction towards e-CBT-I intervention via phone calls will be given to part of the participants in e-CBT-I group after intervention.

Main hypothesis in the present study include:

1. Youth receiving e-CBT-I will have fewer onsets of depressive disorder and higher rates of remission in insomnia disorder at post-intervention, 6-month and 12-month compared

to those in control group.

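### MDD history drives the assumed event rate but is absent from the strata, covariates and reporting, so the MDD result cannot separate first-onset prevention from relapse prevention

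*Combined protocol and SAP*

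**What the plan says.** **Eligibility.** Exclusion criterion 5 removes "The presence of current MDD or a prior episode of MDD within past two months measured by MINI via telephone interview". An older episode does not exclude.

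**Sample Size Estimation.** The starting figure is that "the incidence rate of depression is approximately 11% in the individuals with insomnia". The next step raises it: "As the study sample included a mixture of individuals without prior depression and those with a history of MDD", a 50% increase to 16.5% is expected over one year. No other reason for the increase is given. The expected share with past MDD is not stated.

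**Hypothesis 1 (Study Design).** "Youth receiving e-CBT-I will have fewer onsets of depressive disorder" than controls. The Outcomes section instead names occurrence of MDD, and Data Analysis refers to current MDD and to experiencing a depressive episode. None of these distinguishes a first episode from a recurrence.

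**Strata and covariates.** Randomization is stratified by sex and insomnia severity (Study Design). Data Analysis adds: "Strata variables (sex and insomnia severity) at baseline will be included as covariates in all analyses". MDD is compared by survival analysis and a log-rank test. No subgroup, covariate or sensitivity analysis uses MDD history.

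**The concern.** The plan treats past MDD as important enough to raise the control event rate by half, and then makes no further use of it. This has two consequences.

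- **Interpretation.** Preventing a first depressive disorder and preventing relapse in someone already affected are different claims. The introduction leans on evidence that insomnia precedes the onset of depression, and hypothesis 1 uses the word onsets. A favourable MDD result could come largely from previously depressed youths, and the planned analysis would not show it.
- **Precision.** Leaving out a prognostic factor that the plan itself relies on gives up some precision and leaves chance imbalance in history uncorrected.

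**Working it through.** **Inputs.** From Sample Size Estimation: 11%; 16.5%; hazard ratio 0.5; power 0.80; type I error 0.05 (sidedness not stated, two-sided assumed); 282 evaluable and 354 randomized per arm. Not in the documents: p, the share with past MDD. I assume a range of 0.1 to 0.5.

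**1. The plan's own figure.** The plan requires that "a total of 282 participants per condition would be required to achieve a power of 0.80". Freedman's log-rank formula gives:

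- Events = (1.960 + 0.842)² × [(1 + 0.5)/(1 − 0.5)]² = 7.849 × 9 = 70.6.
- Intervention risk = 1 − (1 − 0.165)^0.5 = 8.62%; mean risk = (16.5% + 8.62%)/2 = 12.56%.
- Per arm = 70.6/(2 × 0.1256) = 281.2, so 282. The figure reproduces.

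With 11% instead of 16.5%, the intervention risk is 5.66%, the mean 8.33%, and the requirement 70.6/(2 × 0.0833) = about 424 per arm. The planned size therefore depends heavily on the history uplift.

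**2. Share of control events that are recurrences.** Let 11% be the one-year risk without prior MDD and r the risk with it:

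(1 − p) × 11% + p × r = 16.5%, so r = 11% + 5.5%/p.

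Share = 1 − (1 − p) × 11/16.5 = 1/3 + 2p/3.

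The share exceeds one third for any p above zero. Because r cannot exceed 100%, p must be at least 5.5/89 = 6.2%, which puts the floor at 37.5%. The share reaches 50% at p = 0.25.

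**3. What a recurrence-only effect would look like.** Suppose recurrences are halved and first onsets are unaffected. The overall risk ratio is then 1 − share/2. The last column is log-rank power (Schoenfeld, two-sided 0.05, 282 per arm). It uses HR = ln(1 − intervention risk)/ln(1 − 0.165) and events = 282 × (sum of the two risks).

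| p | r | Recurrence share | Overall risk ratio | Chance of significance |
|---|---|---|---|---|
| 0.1 | 66% | 40% | 0.80 | 20% |
| 0.2 | 38.5% | 47% | 0.77 | 26% |
| 0.25 | 33% | 50% | 0.75 | 29% |
| 0.3 | 29.3% | 53% | 0.73 | 32% |
| 0.5 | 22% | 67% | 0.67 | 49% |

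**4. Chance imbalance.** With 354 per arm, the 95% limit for imbalance in history is 1.96 × √(2p(1 − p)/354). This is 5.9 points at p = 0.2 and 7.4 at p = 0.5. Multiplied by (r − 11%), it shifts the event-rate contrast by 1.6 and 0.8 points, against a planned contrast of 16.5 − 8.25 = 8.25. The standard error of that contrast is √[(0.165 × 0.835 + 0.0825 × 0.9175)/354] = 2.5 points. The fraction of its variance due to imbalance is (r − 0.11)² × 2p(1 − p)/0.2135: 11% at p = 0.2, 3% at p = 0.5, and 25% at p = 0.1, where the implied r is 66%.

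**5. What a split could show.** At 282 per arm with risk halved in both groups, total events are 282 × (0.165 + 0.0825) = 69.8. First onsets are 69.8 × (1 − share): 34.9 at p = 0.25 and 23.3 at p = 0.5. Power for HR 0.5 among the never depressed is then 50% and 36% (Freedman), or 54% and 39% (Schoenfeld).

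**The case against.** The strongest reply is that the plan never promises first-onset prevention. The outcome is occurrence of MDD, the stated aim is to prevent clinical depression, and the censoring rule refers to any depressive episode. The introduction lists recurrence among the problems and says insomnia raises susceptibility to it. The mixture is disclosed and sized for, and onset can mean the start of any episode. This stands. A reader might infer that the trial fails to answer its stated question, but the documents do not restrict that question to first episodes. What remains is that the wording is not aligned and the reader is left to choose.

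A reader might also infer that the plan's own figures make half or more of the events recurrences. They do not, because p is never given. The one-third figure also rests on 11% being the never-depressed rate. Sample Size Estimation uses it that way, but describes it as the rate in people with insomnia, and the introduction describes the same meta-analysis as covering patients without depression at baseline, which is not the same as never depressed. Writing a for the true never-depressed risk, the share is 1 − (1 − p) × a/16.5%. It is larger if a is below 11% and smaller if a is above.

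A third inference would be bias. Randomization rules that out: imbalance in history is already covered by the type I error. A recurrence-only effect would also more often miss significance than reach it (20% to 49% in the table). Finally, a split by history is too small to settle the matter. That is a reason to label it descriptive, not to omit it.

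**Conclusion.** The point holds as one of interpretation and modest precision. Past MDD is eligible, it is the only reason given for raising the control rate from 11% to 16.5%, and nothing in the strata, covariates or planned reporting uses it. If 11% is the never-depressed rate, more than one third of control events would be recurrences whatever p is, and half or more only if p is at least 25%. The documents do not support a firmer figure. The overall MDD comparison remains valid and the sample size arithmetic is sound. As planned, however, a positive result could not be attributed to first-onset prevention, to relapse prevention, or to both.

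**What to change.** Before any unblinded analysis:

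1. Take prior MDD (yes/no) from the screening MINI.
2. Add it to sex and insomnia severity as a pre-specified covariate in the MDD survival model, or stratify the log-rank test by it.
3. Report the MDD effect separately for participants without and with prior MDD, labelled descriptive and low-powered.
4. In hypothesis 1 and in the conclusions, replace onsets with new episodes (first onset or recurrence).

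The cost is analysis-plan wording and one baseline item; eligibility and sample size do not change. The downsides are imprecise subgroup estimates and a slightly narrower headline claim. One thing must be confirmed first. Exclusion 5 requires asking only about current MDD and the last two months, and the documents do not say that earlier history was recorded. If it was not, the adjustment and the split are not possible. The rewording still applies, and the limitation should be stated.
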